During the test, a piece of sturdy furniture or a standard walker will be placed within the participant's reach to reduce the risk that FOF will contaminate performance and enable even frail people to participate.⁷² In comparison to the age group, the software utilizes the BBS Normative Database to compare the individual to others in their age group. BBS score is dependent on age and sex but not body size so that the percentile rankings can be determined across various age groups, and for men and women separately.⁷³ A scale from 0 to 100 represents the percentile ranking of the BBS. Score 0-30 indicates low fall risk (normal balance) and ≥ 31 moderate-high fall risk (poor balance).⁷³ BBS has excellent validity using Pearson correlations ($r > .90$) and high test-retest reliability [intra-class correlation coefficients (ICC)=0.83].⁴⁵

This test consists of four, 20 seconds trials. For each trial, the participants will stand as still as possible on the BBP with hands on their hips, and eye closed. This test consists of four trials. This test will take about 5-10 minutes (Please see Appendix F for static balance performance test (BTracks Balance System)).

Body composition will be assessed using a bioelectrical impedance analysis (**BIA**): InBody S10. The BIA is a widely used commercial device that is FDA approved. The BIA is manufactured by the Biospace Corporation Limited, Naples, FL. The BIA InBody S10 uses 30 impedance measurements, 6 frequencies at each of the 5 segments (Right Arm, Left Arm, Trunk, Right Leg, Left Leg). The BIA InBody S10 specification: Frequencies: 1, 5, 50, 250, 500, 1000 kHz, Weight Range 22-551 lbs, Age Range 3-99 years, Height Range 3 ft 1.4 in-7 ft 2.6 inch, Equipment Weight 4.4 lbs, and Dimensions 12.7 x 8 x 46.5 (L x W x H) inches with stand

Fig. 4 BIA InBody S10

and Dimensions 8 x 2.1 x 12.7 (L x W x H) inches without stand. The BIA InBody S10 measures fat mass, muscle mass and body water levels. There are no risks, no dunking, no pinching, no discomfort associated with the use of bioelectrical impedance analysis. Test duration is 1-2 minutes. Reliability of the test-retest of the BIA was high with an ICC of 0.89.⁷⁴

Fig. 5 ActiGraph GT9X

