Aim 2 hypotheses are: **1)** Rational FRA is associated with higher levels of PA and skeletal muscle mass, and lower levels of percent of body fat and BMI, **2)** Incongruent FRA is associated with higher levels of PA and skeletal muscle mass, and lower levels of percent of body fat and BMI, **3)** Irrational and congruent FRAs are associated with lower levels of PA and skeletal muscle mass, and higher levels of percent of body fat and BMI. General summary statistics will be presented for continuous data, and percentages will be presented for categorical data. Participant demographic data will be summarized. Analyses will be performed without adjusting for any covariates, followed by the analyses adjusted for age, comorbidities, depressive symptoms, and fall history. Age, the number of comorbidities and the number of falls in the past year will be selected as covariates in the selected model because of their association with FRA, body composition, and PA. Data from InBody770 (e.g., BMI) and ActiGraph (e.g., steps/day) could be modeled as continuous.

Regression models or one-way ANOVA will be used to examine differences in continuous variables (e.g., BMI, steps/day) across the four groups (rational, incongruent, irrational, and congruent FRAs), and categorical variables (e.g., comorbidities) will be tested using Chi-Squared tests. Rational FRA group will set as a base group, and the other three groups (incongruent, irrational, and congruent FRAs) will be compared with this base group. Whenever feasible, models will be adjusted for age, sex, day order, wear time (minutes/day), and the number of fall history. These following variables will add one by one to evaluate the role of each: mobility problems (Y/N), depression (score or category), fall risk (high/low), perceived general health (score of category), medication use (Y/N), and comorbidities (Y/N). A final model will include all significant potential variables to evaluate whether associations between FRA, body composition and PA, whenever feasible.

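### The final Aim 2 model may adjust the fall risk appraisal groups for fall risk (high/low), although physiological fall risk is one of the two axes that define those groups

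*Combined protocol and SAP*

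**What the plan says.** Section 17.1 (Aim 2) sets up the comparison as follows: "Rational FRA group will set as a base group, and the other three groups" are compared with it on body composition and physical activity (PA).

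The models are built in stages. First, "Analyses will be performed without adjusting for any covariates". Adjusted models follow; the base set is age, sex, day order, wear time and fall history. Then six more candidates come in: "These following variables will add one by one to evaluate the role of each". Mobility problems and depression head that list, which continues with "fall risk (high/low), perceived general health (score of category), medication use (Y/N), and comorbidities (Y/N". The last stage is selective: "A final model will include all significant potential variables", where feasible.

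The groups cross two binary axes (Section 6.4, experimental procedures for both groups): short FES-I at most 10 versus above 10, and BBS 0-30 versus 31-100. Section 3.2 describes the balance axis as physiological fall risk and the fear axis as perceived fall risk. The BBS description in Section 6.2 labels the cut-off in the same terms: "Score 0-30 indicates low fall risk (normal balance) and ≥ 31 moderate-high fall risk (poor balance". No other low/high cut-off for fall risk appears in the documents.

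However, Table 1 (Section 6.2) and Section 9.0 list fall risk among the self-report questionnaires, apart from fear of falling and from the balance tests. Section 17.1 does not say which of the two the covariate is.

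**The concern.** A covariate in a model with FRA group as the exposure should not restate part of the exposure. Rational and incongruent differ only in balance; rational and congruent differ in balance and fear of falling. Holding fall risk fixed therefore asks what remains of these contrasts once the physiological half of the group definition has been taken out, which is not what H2.1 to H2.3 ask.

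The interpretation of the final model for the primary objective is at stake. If it contained this term, a small or null coefficient for incongruent or congruent could not be read as no association with FRA.

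**Working it through.** The plan gives no figure on this point, so there is none to reproduce. The documents supply the group definitions and the target of 30 per group, 120 in all (Section 6.4). Agreement between a self-report item and the BBS class is not given and is assumed below.

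**Reading 1: the covariate is the BBS class.** Let I, R and C indicate incongruent, irrational and congruent, with rational as base, and let F = 1 for BBS 31-100. Then F = I + C exactly. The group means in a model with all terms are:

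- rational: b0
- incongruent: b0 + bI + f
- irrational: b0 + bR
- congruent: b0 + bC + f

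There are five coefficients and four means, so the matrix [1, I, R, C, F] with 30 per cell has rank 4 of 5. Only bI + f, bC + f and bR are identified. Hence:

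- incongruent versus rational with fall risk held fixed (bI): not estimable
- congruent versus rational with fall risk held fixed (bC): not estimable
- irrational versus rational (bR): estimable and unchanged
- congruent versus incongruent, (bC + f) - (bI + f): estimable

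Added after the group factor, F contributes 0 degrees of freedom. In a simulated data set of 120, the residual sum of squares was 85.54 both with and without it. A correctly read analysis would find nothing to test.

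The risk lies in what the program drops. Take assumed means of 0 (rational), -0.5 (incongruent), -0.3 (irrational) and -0.9 (congruent). If the congruent indicator is dropped, F receives -0.9, and the coefficient labelled incongruent becomes -0.5 - (-0.9) = +0.4. It then means incongruent minus congruent, with the sign reversed, and F may look like a significant covariate.

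**Reading 2: the covariate is a separate self-report item.** Suppose the item agrees with the BBS class with probability a in every group. The proportion rated high is a in the poor-balance groups and 1 - a in the others, a difference of 2a - 1. With residual variance s² held fixed:

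- Without the item: variance of incongruent versus rational = s²(1/30 + 1/30) = s²/15.
- With the item: s²[1/15 + (2a - 1)²/(120a(1 - a))].
- Variance ratio = 1 + (2a - 1)²/(8a(1 - a)).

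| a | (2a - 1)² | 8a(1 - a) | Variance ratio | SE ratio |
|---|---|---|---|---|
| 0.60 | 0.04 | 1.92 | 1.02 | 1.01 |
| 0.70 | 0.16 | 1.68 | 1.10 | 1.05 |
| 0.80 | 0.36 | 1.28 | 1.28 | 1.13 |
| 0.90 | 0.64 | 0.72 | 1.89 | 1.37 |

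The same ratios apply to congruent versus rational. For irrational versus rational, the proportion rated high is 1 - a in both groups, so the ratio is 1.00.

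The estimate also moves. If g is the item's coefficient in the adjusted model, each poor-balance contrast changes by g(2a - 1): 0.2g at 60% agreement and 0.8g at 90%. The documents do not give g.

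As an illustration only, assume that both instruments classify one underlying binary fall risk with independent errors, that half the sample is truly at high risk, and that the outcome depends on fall risk only through it. With r = 2 × accuracy - 1 for each instrument, the share of the balance contrast retained is (1 - rQ²)/(1 - rB²rQ²), where Q is the questionnaire and B the BBS:

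- BBS 85%, questionnaire 70%: 0.84/0.9216 = 91%
- BBS 85%, questionnaire 85%: 0.51/0.7599 = 67%
- BBS 80%, questionnaire 90%: 0.36/0.7696 = 47%

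**The case against.** The strongest reply is that Section 17.1 leaves the variable undefined, so the plan needs a definition and not a deletion. Several parts of that case stand.

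- **Identity.** A reader might infer that the covariate is the BBS class because it shares the label and the only cut-off. The documents do not establish this: Table 1 and Section 9.0 list a separate self-report item.
- **Which contrasts.** A reader might infer that the trial's central comparison is lost. At most two of the three base-group contrasts are affected. H2.1 and H2.2 put rational and incongruent on the same side, with irrational and congruent opposite under H2.3, so the hypothesised divide follows fear of falling. Irrational versus rational and congruent versus incongruent, the fear contrasts within each balance level, survive even on the BBS reading.
- **Selection.** A BBS term entered after the group factor cannot test significant, so it should not reach the final model unless a group indicator is dropped and the output misread.
- **Other analyses.** The unadjusted and base-adjusted comparisons do not contain the term, and stepwise reporting would show any attenuation beside them.
- **Size.** The loss on the questionnaire reading rests on assumed inputs and runs from slight to large.

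The reply does not rescue the variable in the final model. On the questionnaire reading the significance rule gives no protection: a better measure of fall risk is more likely to be kept and takes out more of the contrast. Naming the instrument settles which problem applies without making either reading a suitable adjustment.

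**Conclusion.** The concern holds, limited to the candidate-covariate step and the final model of Aim 2, and to the incongruent and congruent contrasts with rational. On the BBS reading these two are not estimable (rank 4 of 5); the practical harm comes mainly from misreading output after the program drops a group indicator. On the self-report reading all three contrasts are estimable, but these two are over-adjusted, with standard errors about 1.01 to 1.37 times larger under assumed agreement of 60% to 90%, equal in every group and with residual variance unchanged.

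The documents do not support concluding that FRA cannot be analysed, that all three contrasts fail, or that material attenuation has been shown. Because the unadjusted and base-adjusted results are untouched, this is a change that should be made to the final model, and not a fatal flaw in the study.

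**What to change.** Remove fall risk (high/low) from the candidate covariates of the final models in which FRA group is the exposure, and report it descriptively by FRA group. If its role is of interest and it is a separate questionnaire item, name the instrument and cut-off in Section 17.1 and show the adjusted result only as a labelled sensitivity analysis beside the model without it. If it derives from BBS or the short FES-I, it should not enter any model that already contains FRA group.

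The cost is a short edit to the analysis text; data collection and conduct do not change. The downside is that the final model no longer adjusts for any part of self-reported fall risk that is independent of balance and fear of falling.

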If he/she indicates that she/he is ready and wants to participate in this research study, she/he will be asked to complete the questionnaires such as socio-demographics and fear of falling.

Procedure for contacting participants for timepoint 2:

Experimental procedures for both groups

We will assess the static balance performance using the BBS. Participants will take off their shoes and stand as still as possible on the balance plate with hands on their hips and eyes closed for 2-3 minutes. Participants will then complete the

dynamic balance performance test using the sit to stand by full standing up from a chair as many as possible within 30 seconds.

Participants will be stratified by the FRA matrix.¹⁷ We will continually evaluate across four groups (rational/ incongruent/ irrational/ congruent) to maintain equal cell distribution (30 OAs/group)*.

- 1) rational FRA: low FOF [Short Fall Efficacy Scale International (short FES-I) score ≤ 10] and aligned with normal balance (BBS score = 0-30).
- 2) incongruent FRA: low FOF (short FES-1 score ≤ 10) despite poor balance (BBS score= 31-100).
- 3) irrational FRA: high FOF (short FES-I score > 10) whereas normal balance (BBS score= 0-30).
- 4) congruent FRA: high FOF(short FES-I score > 10) and poor balance (BBS score= 31-100).¹⁷

**Please note: This is not an intervention study and subjects will not be assigned to the study group.*

They will perform the hand-grip strength and sit to stand tests. Hand-grip strength will be measured in kilograms (kg) as maximal isometric force achieved on a hand-grip dynamometer. This test will be administered with participants sitting in a chair with feet flat on the floor and the elbow bent at 90°. The dynamometer will be placed in the hand and adjusted so the palm side of the grip will be at the palm, and the front end will be lined up between the joints of the medial and distal phalanges. The grip size will be adjusted so that the second metacarpals were flat with a 90° bend at the knuckles. Participants will be asked to squeeze the strength gauge as hard as possible for 3–5 seconds. Three trials on each hand will be performed with 30-s of rest given between trials. Participants will complete the sit to stand by full standing up from a chair as many as possible within 30 seconds.⁷⁸

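### Aim 2 specifies comorbidity as a count chosen in advance and also as a yes/no term kept only if significant; one form and one role are needed, and the count fits the plan's own rationale

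*Combined protocol and SAP*

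**What the plan says.** All of the relevant text is in Section 17.1, under Aim 2.

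The first paragraph plans unadjusted analyses, "followed by the analyses adjusted for age, comorbidities, depressive symptoms, and fall history". It then fixes a form for comorbidity: "Age, the number of comorbidities and the number of falls in the past year will be selected as covariates in the selected model". The reason given is that these variables are associated with FRA, body composition and physical activity.

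The second paragraph treats comorbidity differently. For group description, "categorical variables (e.g., comorbidities) will be tested using Chi-Squared tests". The core adjustment omits it: "models will be adjusted for age, sex, day order, wear time (minutes/day), and the number of fall history". It returns in a list of terms to be added singly, which ends with "perceived general health (score of category), medication use (Y/N), and comorbidities (Y/N"). Then: "A final model will include all significant potential variables", where feasible.

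The comparisons at stake are the three FRA groups against the rational group ("Rational FRA group will set as a base group"). Section 6.4 aims "to maintain equal cell distribution (30 OAs/group").

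**The concern.** The same confounder is a count in one paragraph and a yes/no variable in the next. It is chosen in advance in the first and must pass a significance screen in the second. The text does not say whether the selected model of the first paragraph and the final model of the second are the same, so two analysts could both follow the plan and report different adjusted FRA contrasts.

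FRA groups are formed from fear of falling and balance, not by randomisation, so covariate adjustment is the main protection for these contrasts. If the effect of comorbidity rises with the number of conditions, a yes/no term cannot separate one condition from five. Part of any difference in burden between FRA groups would then be credited to FRA. If the term also fails the screen, the final model has no direct comorbidity adjustment.

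**Working it through.** **The text.** Set side by side:

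| | First paragraph | Second paragraph |
|---|---|---|
| Form | number of comorbidities | yes/no |
| Role | covariate chosen in advance | candidate, kept if significant |
| Model | selected model | final model |

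This conflict needs no calculation. The plan states no comorbidity figure, so there is none to reproduce; the rest rests on stated assumptions.

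**Share of confounding left by yes/no.** Assume two equal groups with Poisson counts of mean μ and μ + Δ, an outcome effect linear in the count, no true FRA effect and no other covariates. Take Δ as 0.5 or 1, and choose μ to give the assumed overall prevalence of at least one comorbidity.

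Let a = e^(−μ) and b = e^(−(μ+Δ)) be the proportions with none. Let t0 = μ/(1−a) and t1 = (μ+Δ)/(1−b) be the mean counts among those with at least one. In least squares, the group coefficient given yes/no is a weighted average of the within-stratum differences. The weights are w0 = ab/(a+b) for none and w1 = (1−a)(1−b)/(2−a−b) for any. The difference in the none stratum is zero, so

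share left = [w1/(w0+w1)] × (t1−t0)/Δ.

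Example at 80% prevalence, Δ = 1:
- μ = 1.23, a = 0.292, b = 0.108
- t0 = 1.738, t1 = 2.498
- w0 = 0.0786, w1 = 0.3947
- share = 0.834 × 0.761 = 0.63

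| Any comorbidity (assumed) | Expected with none, of 120 | Left by yes/no, Poisson | Left by yes/no, overdispersed (negative binomial, shape 2) |
|---|---|---|---|
| 50% | 60 | 31–32% | 42% |
| 70% | 36 | 49–52% | 62–63% |
| 80% | 24 | 61–63% | 73% |
| 90% | 12 | 75–77% | 85% |
| 95% | 6 | 85–86% | 92% |

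Adjusting for the count leaves none, by construction, because the effect is assumed linear in it.

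**The significance screen.** Simulated samples of 120 with Poisson counts, the count correlating 0.2 to 0.3 with the outcome, and each coding tested alone at p<0.05 (2,000 runs per setting):

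| Any comorbidity (assumed) | Yes/no significant |
|---|---|
| 50% | 45–79% |
| 80% | 28–55% |
| 90% | 18–38% |

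The count is significant in about 59–93% of samples at any of these prevalences. It would therefore still be lost in about 7–41%, so changing the coding alone does not settle the role.

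**Size against sampling error.** Assume 300 steps/day lost per condition, a gap of one condition between groups and a residual SD of 2,500 steps/day; none of these is in the documents. Unadjusted bias is 300 × 1 = 300 steps/day. Yes/no leaves 0.63 × 300 ≈ 190 at 80% prevalence and 0.77 × 300 ≈ 231 at 90%. With 30 per group the standard error is at least 2,500 × √(2/30) = 645 steps/day, and about 665 after adjustment at these prevalences. The leftover bias is about 190/665 = 0.29 to 231/665 = 0.35 standard errors. In simulation at these prevalences and above, the false-positive rate under yes/no is about 6–7%, against 5% with the count.

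**The case against.** A reader might infer that yes/no is close to constant in this population, so that most comorbidity confounding would remain. The documents do not support that. They give no prevalence or mean count. Section 10.2 excludes people with conditions that preclude the balance test or physical activity, those in rehabilitation treatment and those with a metal implant. It sets no income criterion, and Section 13 also recruits from the general population. More than half of the confounding remains only if prevalence is roughly 70% or more with Poisson counts, or 60% or more with overdispersed counts.

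Four further objections have force:
- Linearity is assumed. If only any versus none matters, yes/no is sufficient.
- The calculation has no other covariates. Age, sex and fall history are adjusted for, and mobility problems, depression, perceived health and medication use are candidates. Any that are retained may carry part of the comorbidity burden.
- The first paragraph still plans an adjusted analysis and names the count for its selected model. A reader might infer that comorbidity will go unadjusted altogether; the text does not say so.
- At 30 per group the bias is small beside the standard error.

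These limit the size of the problem. They do not reconcile the two specifications, and none is a reason to prefer yes/no over the count that the plan already chose.

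**Conclusion.** The point holds as a conflict of form and role with a conditional cost. That Section 17.1 specifies comorbidity in two incompatible ways is certain from the text. That yes/no discards the gradient named as the reason for adjustment follows directly. The amount of confounding left, from about 32% at 50% prevalence to 75% or more at 90%, rests on an assumed prevalence, Poisson counts, a linear effect and no other covariates. The effect on inference at the planned group size is likely to be modest. It should be corrected because the result depends on which paragraph is followed and the remedy is nearly free; it does not by itself undermine Aim 2.

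**What to change.** In Section 17.1, replace the yes/no comorbidity term in the one-by-one list with the number of comorbidities. State that it is chosen in advance, is not subject to the significance screen, and enters every adjusted Aim 2 model, including the final one. Say whether the selected model and the final model are the same. Use yes/no only in descriptive tables. State the counting rule, and confirm that the Appendix A survey (not in the text available for this review) records conditions in a way that allows a count.

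The cost is a phrase and two or three sentences. Comorbidities are already collected by self-report questionnaire (Table 1). The count uses one degree of freedom, the same as yes/no; retaining it regardless of significance costs at most that one degree of freedom among 120 participants.

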1.0 Study Summary

Study Title	Technology-based fall risk assessments for older adults in low-income settings
Study Design	We will use a cross-sectional design to address our aims and test hypotheses.
Primary Objective	Examine the associations among fall risk appraisal, body composition, and physical activity.
Secondary Objective(s)	-Examine the feasibility of recruitment (e.g., how many older adults (OAs) need to be screened to recruit the sample?), especially during the COVID-19 pandemic, and acceptability of technologies and procedures for use among OAs in low-income settings. -Determine the dynamic relationships between fall risk appraisal, body composition, physical activity, and behavioral changes related to fear of falling
Research Intervention(s)/ Investigational Agent(s)	NA
IND/IDE #	NA
Study Population	Adults aged 60 years and older
Sample Size	120 participants for timepoint 1 60 participants for timepoint 2
Study Duration for individual participants	Total 9 days with two visits (105-158 mins, total)
Study Specific Abbreviations/ Definitions	Older Adults (OAs) Physical Activity (PA) Fall Risk appraisal (FRA) Fear of Falling (FOF) Assistive Health Technology (AHT) BTrackS Balance Plate (BBP) BTrackS Balance System (BBS) Body Mass Index (BMI) Bioelectrical Impedance Analysis (BIA) Fall-Efficacy Scale International (FES-I) Patient Health Questionnaire-9 (PHQ-9)

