5.0 Study Intervention/Investigational Agent NA

6.0 Procedures Involved*

6.1 Describe and explain the study design.

We will use a cross-sectional design to address our aims and test hypotheses. Using novel technologies to advance fall risk assessments is one of the essential recommendations for promoting PA.^{47, 48 17, 37, 41, 49} To accomplish this goal, we employ the behavioral epidemiology framework⁵⁰ to understand

the associations among body composition, FRA, and PA.

This framework consists of 5 phases: (1)

establish links between behaviors and health, (2) develop measures of the behaviors, (3) identify influences on the behaviors, (4) evaluate interventions to change the behavior, and (5) translate research into practice.⁵⁰ We focus on Phase 1 and in our model, body composition is an antecedent of FRA and the accelerometer-based PA is a consequence of FRA. We consider OAs' characteristics (e.g., sex) as covariates and control for them in the analysis (Fig 2).

[figure not shown]

Fig. 2 Conceptual Framework

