6.2 Provide a description of all research procedures

We will administer the study instruments which consist of objective and subjective measures (see Table 1) for total 120 participants. Participants will complete questionnaires about OA's characteristics, socio-demographic, medical history, cognition, depressive symptoms, anxiety,

and FOF. We will also assess static balance performance using the BTrackS Balance System^{43, 44}, assess dynamic balance using a sit to stand test, assess body composition using the Bioelectrical Impedance Analysis device⁴², and assess handgrip strength test using a hand-grip dynamometer (JAMAR 5030J1). They will wear an accelerometer-based physical activity device for 7 consecutive days.

Table 1. Description of study variables and instruments

Variable	Instrument	Description
OA's Characteristics - Socio-demographics and medical history -Cognition - Depressive symptoms -Anxiety and day-to-day experiences	Self-report questionnaire - Memory Impairment Screen (MIS) ⁵¹⁻⁵³ -Patient Health Questionnaire-9 (PHQ-9) ^{54, 55} -Geriatric Anxiety Inventory-Short form (GAI-SF). ⁵⁶⁻⁵⁸	e.g., age, gender, living status, education level, socioeconomic status, perceived general health, comorbidities, FOF, frailty, fall risk, and social network. - The Memory Impairment Screen (MIS) is a widely used test of cognitive function and screening Alzheimer's disease among OAs. It is a 4-minute, four-item delayed free and cued recall memory test with controlled learning and high discriminative validity. The maximum score for the MIS is 8 and if score 5-8=no cognitive impairment and score ≤ 4 =possible cognitive impairment. -10 items (e.g., feeling tired) on a 4-point scale; measures symptoms of depression within the prior 2 weeks; Total scores range 0-27, scores ≥ 10 moderate depression. ⁵⁴ Cronbach's alpha=0.89 among OAs. ^{54, 55} - The GAI-SF is an abbreviated version of GAI comprising only five of the original items. The GAI-SF has good internal consistency, convergent and divergent validity, and was highly

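### Aim 2 (primary objective): the final model keeps candidate covariates only if significant, depression and comorbidities are both adjusters and droppable candidates, and no model is designated primary

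*Combined protocol and SAP*

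**What the plan says.** Section 1.0 gives the primary objective as "Examine the associations among fall risk appraisal, body composition, and physical activity". This is Aim 2, with hypotheses H2.1 to H2.3. The Aim 2 analysis text in section 17.1 runs in this order:

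1. Unadjusted analyses come first, "followed by the analyses adjusted for age, comorbidities, depressive symptoms, and fall history".
2. Next: "Age, the number of comorbidities and the number of falls in the past year will be selected as covariates in the selected model". The reason given is that these are related to FRA, body composition and PA.
3. The four FRA groups are compared by regression or one-way ANOVA, with rational FRA as reference. "Whenever feasible, models will be adjusted for age, sex, day order, wear time (minutes/day), and the number of fall history".
4. Six further variables are entered one at a time: "mobility problems (Y/N), depression (score or category), fall risk (high/low), perceived general health (score of category"), followed by medication use and comorbidities, both coded Y/N.
5. Last: "A final model will include all significant potential variables to evaluate whether associations between FRA, body composition and PA, whenever feasible".

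The text names no test and no p-value for keeping a variable. The only significance level in the document, two-sided 0.05, is in the sample-size paragraph for Aim 2. No sentence says which of these models tests H2.1 to H2.3.

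**The concern.** The study compares four observed groups, so the answer to Aim 2 depends on how confounding is handled. Under the rule as written, part of the adjustment set is decided by the data, separately for each outcome. A variable that truly confounds the FRA comparison is left out whenever its own p-value misses an unstated cut-off, and its confounding then stays in the FRA contrast.

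The covariates named in advance do not settle the matter. Depression and comorbidities are among them, yet both return as candidates that can be dropped. Because no model is designated primary, the unadjusted, adjusted and final results could disagree with nothing to say which one answers the aim.

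**Working it through.** The plan gives no figure on this point to reproduce. Its relevant inputs are N=120 and 30 participants per FRA group (section 6.4). Everything about confounding below is an assumption.

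**Roles of the variables in section 17.1**

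| Variable | First adjusted list | Selected model | Whenever-feasible list | Droppable candidate |
|---|---|---|---|---|
| Age | yes | yes | yes | no |
| Fall history | yes | yes (number) | yes (number) | no |
| Comorbidities | yes | yes (number) | no | yes (Y/N) |
| Depression | yes | no | no | yes (score or category) |
| Sex, day order, wear time | no | no | yes | no |
| Mobility, fall risk, perceived health, medication | no | no | no | yes |

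Only age and fall history appear in every list and are never candidates. If all six candidates can drop, there are 2^6 = 64 possible final models per outcome. If comorbidities are always kept there are 2^5 = 32, and if depression is kept too, 2^4 = 16.

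**How often a real confounder is kept.** Take a model with FRA group, age, sex, falls, wear time and one candidate. Residual df = 120 - 1 - 3 - 4 - 1 = 111. For an effect of b SD per SD, the expected t is about b x sqrt(111) = 10.54b, and the chance of p<0.05 is about Phi(10.54b - 1.98).
- b = 0.15: Phi(1.58 - 1.98) = Phi(-0.40), about 34%.
- b = 0.25: Phi(2.63 - 1.98) = Phi(0.65), about 74%.

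Simulation gave 30-35% and 65-73%. Confounders not yet in the model add residual spread, which lowers the rates a little.

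**What omission costs.** Omitting one confounder shifts the contrast by (group shift) x b: from 0.5 x 0.15 = 0.075 SD to 0.8 x 0.25 = 0.20 SD. The standard error of a 30-versus-30 contrast is about sqrt(2/30) = 0.258 SD.

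**Simulation.** 4,000 runs per setting; no true FRA effect; person-level outcome; core of age, sex, falls and wear time. Five candidates were used: mobility and medication as Y/N; depression, perceived health and comorbidities as scores. Fall risk was left out. Confounders were shifted 0.5 or 0.8 SD in the two high-FOF groups and lowered PA by 0.15 or 0.25 SD per SD. Three confounder sets were used: (1) depression and comorbidities; (2) these plus perceived health; (3) mobility, perceived health and medication. Each candidate was tested alone with core and FRA, and those with p<0.05 entered the final model. Type I error for irrational versus rational FRA (Monte Carlo SE 0.3-0.5 points for the selection results):

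| Approach | Sets 1-2 | Set 3 |
|---|---|---|
| All five droppable | 6.3-13.0% over all three sets | (same range) |
| Comorbidities always kept | 5.4-8.5% | 7.2-12.2% |
| Comorbidities and depression always kept | 4.6-6.2% | 7.1-12.0% |
| All five fixed | 4.5-5.5% over all three sets | (same range) |
| Only core + depression + comorbidities fixed | 4.6-9.7% | 10.4-42.3% |

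Repeat runs with separate code and fewer replicates put the first row's upper end at 14.1-14.3%, and the second and third rows' sets 1-2 upper ends at 10.2% and 8.0%. Bias with all five droppable was -0.04 to -0.16 SD; with all five fixed it was at most 0.02 SD. Looser retention shrinks the first row to 5.8-10.2% (p<0.10) and 5.4-8.2% (p<0.20). With no confounding, every approach stays at 5.1-5.8%.

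**Effect of not designating a primary model.** In a separate simulation with six candidates unrelated to FRA, each single model rejected in about 5% of runs. Taking the smallest p-value across five models (unadjusted, all fixed, and selection at 0.05, 0.10 and 0.20) rejected in about 8%.

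**The case against.** Much can be said for the plan. The text is partly a staged sequence: unadjusted, adjusted, then further variables in turn. The second list directly follows the first and reads as its rationale, and wear time and day order belong to accelerometer outcomes. The final-model sentence ties that model, loosely, to Aim 2. An alpha of 0.05 does appear under Aim 2, although applying it to covariate retention would be an inference. The largest bias, 0.16 SD, is 0.16/0.258 = 0.62 of a standard error, and every confounding strength is assumed. All this stands and limits the size of the point. It does not remove the retention rule, the double role of two covariates or the two codings of comorbidities.

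A further objection also stands: fixing too small a set can be worse than selection. If mobility, perceived health and medication confound and are left out, the error is 10.4-42.3%, against 7.1-12.0% under selection with comorbidities and depression kept.

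Three stronger readings are tempting but not supported:
- A reader might infer that section 6.1 contradicts section 17.1, because it treats participant characteristics "as covariates and control for them in the analysis". Section 6.1 gives sex as an example and sets no list or rule, and section 17.1 does adjust for sex.
- A reader might infer that the fall-risk candidate is the BBS class that defines the FRA groups, and so is collinear with them. Table 1 lists it with self-reported characteristics ("perceived general health, comorbidities, FOF, frailty, fall risk, and social network"), so a questionnaire item is the likelier source.
- A reader might infer that the most favourable model will be reported. The plan does not say so; the 8% figure shows only what such a choice would cost.

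**Conclusion.** The point holds in this form. For the primary objective, adjustment is chosen partly by significance with no threshold tied to the rule; depression and comorbidities are both adjusters and droppable; comorbidities have two codings; and no model is designated primary. These are facts of the text and need no simulation.

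The size is illustrative. Type I error for irrational versus rational FRA is about 6-14% if all five non-fall-risk candidates can drop at p<0.05. It is lower if comorbidities and depression are always kept and are among the confounders, and about 5% with all five fixed. It rests on assumed shifts of 0.5-0.8 SD and effects of 0.15-0.25 SD per SD, complete data and equal groups of 30. If there is no confounding, selection does no harm to the error rate. This should be corrected before analysis, but it does not make the study uninterpretable.

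**What to change.** Delete the significance-based retention rule. Before analysis, designate one primary adjusted model per outcome, reported whatever the p-values: FRA group (rational as reference), age, sex, number of falls, number of comorbidities and PHQ-9 score, with one coding each, plus wear time for accelerometer outcomes. Day order is needed only if daily records are modelled.

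Also before analysis, classify mobility problems, perceived general health and medication use on subject-matter grounds. Confounders enter the primary model; possible consequences of FRA do not. Always report the model with all three added as a fixed sensitivity analysis, whatever the classification. Label the unadjusted and one-by-one models, including fall risk, as sensitivity analyses.

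**Cost.** Only the analysis text changes; the variables are already in the plan. Residual df for accelerometer outcomes are 120 - 1 - 3 - 4 = 112 with the core, 110 with comorbidities and depression, and 107 with the three extra variables; for body composition, without wear time, 113, 111 and 108. Compared with p<0.05 selection, the standard error of the FRA contrast is 0-6% larger with comorbidities and depression fixed and 2-9% larger with all five.

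Over-adjustment is the main downside. If mobility problems and perceived health are consequences of fear of falling, including both removes about 0.13-0.36 SD of a true association under the same assumed strengths. Depression could also be such a consequence, so its place in the primary model needs a recorded justification too.
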